b. Responders who are not eligible to enter the randomized downtitration will continue on the treatment regimen assigned at baseline; however, rerandomization to either 4-mg or 2-mg baricitinib is available for the placebo, baricitinib 2-mg, and 1-mg treatment groups if patients have a worsening of symptoms.

c. Nonresponders in the placebo, baricitinib 2-mg, or baricitinib 1-mg treatment groups will be rerandomized at a 1:1 ratio to baricitinib 4-mg or baricitinib 2-mg QD at Week 52. After rerandomization, patients will remain on the same dose of baricitinib for the remainder of the study. Nonresponders who were randomized to baricitinib 4-mg will remain on 4-mg.

Period 4: Bridging Extension: from Week 104 (Visit 22) and up to Week 200 (Visit 28). Subjects who have completed Week 104 and have not met criteria of permanent discontinuation will have the possibility to remain in the trial for up to 96 additional weeks (up to Week 200).

Period 5: Post-Treatment Follow-Up Period: from last treatment period visit or early termination visit (ETV) to 4 weeks after the last dose of investigational product.

Treatment Arms and Duration:

At baseline, patients will be randomized at a 1:1:2:1 ratio to receive placebo QD, baricitinib 1-mg QD, baricitinib 2-mg QD, or baricitinib 4-mg QD for up to 200 weeks.

Number of Patients:

Planned enrollment is 500 patients ≥ 18 years of age.

Statistical Analysis

Unless otherwise specified, the efficacy and health outcome analyses will be conducted on the intent-to-treat population and safety analyses will be conducted on those patients who receive at least 1 dose of investigational product.

Treatment comparisons of discrete efficacy variables will be made using a logistic regression analysis with treatment, baseline disease severity (vIGA AD) and baseline score in the model. Region may be added to the model if patient numbers allow. The proportions and 95% confidence interval (CI) for the treatment comparisons will be reported. If a patient needs to use rescue medication, the data from that point forward will be considered missing and missing data will be imputed using the nonresponder imputation (NRI) method. Additional analyses will be conducted using all observed data regardless of whether rescue medication was used or not.

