10.2. Populations for Analyses

Unless otherwise specified, the efficacy and health outcome analyses will be conducted on the intent-to-treat population, defined as all randomized patients, even if the patient does not receive the correct treatment, or otherwise did not follow the protocol.

Unless otherwise specified, safety analyses will be conducted on all randomized patients who receive at least 1 dose of investigational product they were randomized to in Study JAIN and who did not discontinue from the study for the reason “Lost to Follow-up” at the first postbaseline visit.

Patients will be analyzed for efficacy, health outcomes, and safety according to the treatment to which they were assigned. Further details will be described in the SAP, including but not limited to, additional populations for the randomized down-titration substudy. Significant protocol violations will be described in the SAP.

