#### 6.2.1. Analysis Populations

The following major analysis populations will be used in SAP for the analysis (additional analysis populations for specific analysis will be defined in the corresponding analysis section):

**Intent-to-treat (ITT) population:** The ITT population analysis set is defined as all randomized patients..

**Per-protocol Set (PPS):** The PPS of the ITT population analysis set will include those patients who are not deemed noncompliant with treatment in Period 2 (up to Week 52), who do not have significant protocol violations, and whose investigator site does not have significant good clinical practice (GCP) issues that require a report to the regulatory agencies prior to Week 16 (Visit 8). Qualifications for and identification of significant protocol deviations will be determined while the study remains blinded, prior to DBL. Details can be found in Section [6.15](#).

Unless otherwise specified, the efficacy and health outcome analyses for Period 2 will be conducted on the ITT population (Gillings and Koch 1991), which seeks to preserve the benefits of randomization and avoids the issue of selection bias. Patients will be analyzed according to the treatment to which they were assigned, even if the patient does not receive the correct treatment, or otherwise did not follow the protocol. In addition, the primary and key secondary analyses will be repeated using the PPS population.

**Safety population:** The safety population is defined as all randomized patients at Visit 2 who receive at least 1 dose of investigational product and who did not discontinue from the study for the reason 'Lost to Follow-up' at the first postbaseline visit. This definition excludes patients with no safety assessments postbaseline so that incidence rates are not underestimated.

Safety analyses will be done using the safety population. Patients will be analyzed according to the treatment regimen to which they were assigned. Analyses of the safety endpoints, many of which are incidence based, will include all patients in the safety population, unless specifically stated otherwise. In the rare situation where a patient is lost to follow-up at the first postbaseline visit but some safety data exist (for example, unscheduled laboratory assessments) after first dose of study drug, a listing of the data or a patient profile will be provided when requested.

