### 6.13.1. Adverse Events

Adverse events are recorded in the eCRFs. Each AE will be coded to System Organ Class (SOC) and Preferred Term (PT) using the Medical Dictionary for Regulatory Activities

(MedDRA) version that is current at the time of DBL. Severity of AEs is recorded as mild, moderate, or severe.

A treatment-emergent adverse event (TEAE) is defined as an event that either first occurred or worsened in severity after the first dose of study treatment and on or prior to the last visit date during the analysis period. The analysis period is defined as the treatment period plus up to 30 days off-drug follow-up time.

Adverse events are classified based upon the MedDRA PT. The MedDRA Lowest Level Term (LLT) will be used in defining which events are treatment-emergent. The maximum severity for each LLT during the baseline period up to first dose of the study medication will be used as baseline. If an event with missing severity is pre-existing during the baseline period, and persists during the treatment period, then the baseline severity will be considered mild for determining treatment-emergence (that is, the event is treatment-emergent if the severity is coded moderate or severe postbaseline and not treatment-emergent if the severity is coded mild postbaseline). If an event occurring postbaseline has a missing severity rating, then the event is considered treatment-emergent unless the baseline rating is severe, in which case the event is not a treatment-emergent. The day and time for events where onset is on the day of the first dose of study treatment will both be used to distinguish between pretreatment and posttreatment to derive treatment-emergence. Should there be insufficient data for AE start date to make this comparison (for example, the AE start year is the same as the treatment start year, but the AE start month and day are missing), the AE will be considered treatment-emergent.

In general, summaries will include the number of patients in the safety population (N), frequency of patients experiencing the event (n), and relative frequency (that is, percentage;  $n/N*100$ ). For any events that are gender-specific based on the displayed PT, the denominator used to compute the percentage will only include patients from the given gender.

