For selected safety topics, incidence rate (IR) per 100 patient-years of observation (PYR) will be provided for the Week 52, Week 104, and final analyses. See the Compound level safety standards for more details.

Adverse Events and Treatment Emergent AEs will be replicated based on the Safety Censoring rule 1 and 2.

Safety censoring rule 1 excludes the event if it's after the permanent study drug discontinuation, or dose change, whichever occurred earlier and Safety censoring rule 2 excludes the event if it's after the permanent study drug discontinuation.

Extended Safety Analysis includes patients who were continuously treated with Baricitinib 1mg, 2mg, or 4mg and Placebo from baseline and censored in case of dose change using Safety Censoring Rule 1. In addition to the above treatment groups “ALL BARI” will also be included to the summary which includes patients who received at least one dose (1 mg, 2mg, or 4mg) of BARICITINIB at any time of the treatment period.

In an overview table, the number and percentage of patients in the safety population who experienced death, an SAE, any TEAE, discontinuation from the study due to an AE, permanent

discontinuation from study drug due to an AE, TEAEs which are considered related to treatment by the investigator, or a severe TEAE will be summarized by treatment group.

The number and percentage of patients with TEAEs will be summarized by treatment group in 2 formats:

- by MedDRA PT nested within SOC with decreasing frequency in SOC, and events ordered within each SOC by decreasing frequency in the All baricitinib group
- by MedDRA PT with events ordered by decreasing frequency in the All baricitinib group.

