- **Treatment-emergent high/low analyses:** The number and percentage of patients with treatment-emergent high and low laboratory results at any time will be summarized by treatment group. Planned and unplanned measurements will be included. A treatment-emergent **high** result is defined as a change from a value less than or equal to the high limit at all baseline visits to a value greater than the high limit at any time during the treatment period. A treatment-emergent **low** result is defined as a change from a value greater than or equal to the low limit at all baseline visits to a value less than the low limit at any time during the treatment period. The Fisher's exact test will be used for the treatment comparisons.

For laboratory analyte measurements collected qualitatively, a listing of abnormal findings will be provided. The listing will include but not be limited to patient identifier (ID), treatment group, laboratory collection date, analyte name, and analyte finding. If needed by the safety physician/scientist, for analytes measured qualitatively, the number and percentage of patients with treatment-emergent abnormal laboratory results at any time will be summarized by treatment. Planned and unplanned measurements will be included. A treatment-emergent abnormal result is defined as a change from normal at all baseline visits to abnormal at any time postbaseline.

The listing of specific reference ranges used in analysis of laboratory data will be provided.

Note that additional analyses of certain laboratory analytes will be discussed within subsections of Section 6.13.4 pertaining to Special Safety topics (Section 6.13.4.1 for hepatic analytes, Section 6.13.4.2 for analytes related to hematologic changes, Section 6.13.4.3 for analytes related to lipids, Section 6.13.4.4 for analytes related to renal function, and Section 6.13.4.5 for creatine phosphokinase [CPK]).

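### The safety population drops some dosed patients by their reason for leaving, not by absence of post-dose safety data

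*SAP*

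**What the plan says.** SAP 6.2.1 builds the safety population from randomised patients with at least one dose and then removes some of them. It keeps only those "who did not discontinue from the study for the reason 'Lost to Follow-up' at the first postbaseline visit". Protocol 10.2 uses the same test: "who did not discontinue from the study for the reason “Lost to Follow-up” at the first postbaseline visit".

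The SAP gives its reason: "This definition excludes patients with no safety assessments postbaseline so that incidence rates are not underestimated". It then names an exception, "In the rare situation where a patient is lost to follow-up at the first postbaseline visit but some safety data exist", with unscheduled laboratory tests as its example. For that case it offers a listing or a patient profile if someone asks for one. It does not return the patient to the population.

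SAP 6.13.1 makes the safety population the N of the adverse event percentages. For patients inside the population, the treatment-emergent high/low laboratory analysis in SAP 6.13.2 counts extra tests: "Planned and unplanned measurements will be included". For selected topics, an "incidence rate (IR) per 100 patient-years of observation (PYR) will be provided for the Week 52, Week 104, and final analyses".

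**The concern.** The aim is about missing data; the rule is about a coded reason for leaving. The two usually coincide. When they do not, a dosed patient with a recorded post-dose event is in neither the numerator nor the denominator. The exclusion was written so that incidence would not be understated, and in this one case it understates incidence.

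What is at stake is limited: a non-serious treatment-emergent event, or a laboratory abnormality, in a patient lost at about Week 1. The point concerns the completeness of the safety tables, not efficacy.

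**Working it through.** **1. Rule against aim.** For dosed patients there are three cases:

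| Patient | Rule in 6.2.1 | Stated aim |
|---|---|---|
| Lost to follow-up at first postbaseline visit, no data | out | out |
| Lost to follow-up at first postbaseline visit, some post-dose data | out | in |
| Left early for another reason, no data | in | out |

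The second row is the exception the SAP names. The third row is only a theoretical gap, because protocol 5.1.5, 8.1.2 and 8.2 call for an early termination visit or safety follow-up from patients who stop early.

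**2. Where such data would come from.** In the Schedule of Activities the first postbaseline visit is Visit 3 (Week 1). The next scheduled chemistry and haematology after baseline are at Visit 5 (Week 4). A laboratory value for a patient lost at Visit 3 is therefore unscheduled, which fits the SAP's own example. Protocol Appendix 2 allows such tests at the investigator's discretion. SAP 6.2 says that unscheduled data are listed and are used in categorical safety analyses. It does not change who belongs to the safety population.

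**3. Size for percentages.** The plan gives no count or rate on this point, so there is no figure to reproduce. Inputs: 100 patients each on placebo, 1 mg and 4 mg, and 200 on 2 mg (protocol 5.1). Assumptions: all are dosed, and exactly one patient in the arm is excluded although he or she has the event. With x events among the others, the table shows x/(N − 1) now and (x + 1)/N with the patient included:

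| N | x | Now | Included | Change (points) |
|---|---|---|---|---|
| 100 | 0 | 0/99 = 0.00% | 1/100 = 1.00% | +1.00 |
| 100 | 9 | 9/99 = 9.09% | 10/100 = 10.00% | +0.91 |
| 100 | 59 | 59/99 = 59.60% | 60/100 = 60.00% | +0.40 |
| 200 | 0 | 0/199 = 0.00% | 1/200 = 0.50% | +0.50 |
| 200 | 19 | 19/199 = 9.55% | 20/200 = 10.00% | +0.45 |
| 200 | 119 | 119/199 = 59.80% | 120/200 = 60.00% | +0.20 |

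The change is (N − 1 − x)/[N(N − 1)], which is largest at x = 0, where it equals 1/N. For the 100 + 200 + 100 = 400 patients first randomised to baricitinib, the ceiling is 1/400 = 0.25 point.

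**4. The opposite direction.** If an added patient has no event, the percentage goes from x/(N − 1) to x/N. With N = 100: 1/99 = 1.01% to 1.00%; 10/99 = 10.10% to 10.00%; 60/99 = 60.61% to 60.00%.

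**5. Rates per 100 patient-years.** Assume 99 patients followed for 364 days: 99 × 364/365.25 = 98.66 patient-years. A patient lost at Day 7 adds 7/365.25 = 0.019, giving 98.68. If that patient has the only event, the rate is 0 without the patient and 100 × 1/98.68 = 1.013 with. If the only event is in someone else, the rate moves from 1.0136 to 1.0134.

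**The case against.** The strongest reply is that this is a disclosed and consistent choice. Protocol 10.2 and SAP 6.2.1 agree, and the SAP states its purpose, names the exception, calls it rare and says how it will be handled. Protocol 8.3 defines lost to follow-up as repeated failure to return plus inability to make contact, which is a fair proxy for having no data. The patient must also have an event, recorded within roughly a week of first dose.

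Most serious information is reported by other routes. All serious events and deaths are listed (SAP 6.13.1.2), as are events leading to discontinuation and all drug interruptions (6.13.1.3) and events sent for adjudication (6.13.4.7 and 6.13.4.8). Notable events get narratives (6.13.1.4), marked liver enzyme elevations get profiles (6.13.4.1), and the registry summary counts serious events whether or not they are treatment-emergent (6.19). All of this stands, and it makes the point small. It does not put a non-serious event or an ordinary laboratory abnormality back into the tables.

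Two stronger readings are tempting, and the documents support neither.

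- A reader might infer that the protocol contradicts itself, because the synopsis says "safety analyses will be conducted on those patients who receive at least 1 dose of investigational product" with no exclusion. That sentence opens by allowing for other specification, and section 10.2 then specifies otherwise. It is a short summary that yields to the full text.
- A reader might infer that every safety record of such a patient disappears from the summaries. SAP 6.13.4.10 takes all reported malignancy cases into its summary analyses, whatever the gap from last dose, and the listings above have no such exclusion stated.

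**Conclusion.** The rule does not match its stated aim in the one case the SAP itself identifies. There, a dosed patient with post-dose safety data is left out of the safety-population summaries, and SAP 6.2.1 guarantees only a listing or profile on request. The exposure is mainly to non-serious adverse events and unscheduled laboratory abnormalities.

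The frequency cannot be derived from the documents beyond the word rare. The ceilings above, 1 point in a 100-patient arm and 0.5 in the 200-patient arm, rest on the assumption of one affected patient who has the event and no other case in the arm. They shrink for common events, and they are zero if no such patient exists. Nothing in the documents suggests that the loss would differ between arms. This is a minor improvement, not a flaw that threatens a conclusion.

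**What to change.** Keep the exclusion in SAP 6.2.1, but apply it only to a patient who was lost to follow-up at the first postbaseline visit *and has no post-dose safety record*. Delete the sentence offering a listing or profile on request, which is then unnecessary. Align protocol 10.2, or explain the change in the clinical study report if the sponsor judges that it is not a principal feature (protocol 10.3.1). List by patient anyone whose population flag differs from the earlier locks.

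A safety set based on dosing alone is not recommended. It would bring back the patients with no data whom the sponsor deliberately removed. For an event with 60% incidence in a 100-patient arm, one such patient lowers the percentage by 0.61 point, more than the 0.40 point gained from one rare patient with the event.

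The cost is one clause and one population flag. There are two downsides. SAP Version 5 serves the final lock, so denominators may move by a patient or two against the 24-, 52- and 104-week locks. Admitting patients because they have a record also leans very slightly towards overstating incidence, since a record is more likely when something happened. If no such patient exists, no number changes.

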^c Patients for whom PPD skin test for the evaluation of TB infection was performed at V1 must return and PPD test must be read 48 to 72 hours after Visit 1 (post-PPD).

^d At Visit 2 (W0) and up to Visit 22 (W104), patients will be supplied with mild- and moderate-potency TCS to be applied per the guidelines in Section 7.7.2.

^e At Week 52, responders (IGA 0 or 1) and partial responders (IGA 2) who were assigned to baricitinib 4-mg or 2-mg, at randomization, are currently receiving investigational product (does not currently have study drug interrupted), and have not used high- or ultra-high-potency TCS in the previous 14 days will be enrolled into the downtitration substudy. If a patient in the substudy has an IGA ≥3 during Periods 3 or 4, they will be retreated automatically with their presubstudy baricitinib dose for the remainder of the study.

^f At Week 52, responders (IGA 0 or 1) and partial responders (IGA 2) in the baricitinib 4-mg or baricitinib 2-mg treatment groups who are not eligible for the randomized downtitration substudy and those who are in the baricitinib 1-mg or placebo groups will remain on their current dose of investigational product. If worsening of AD symptoms occurs any time during Periods 3 or 4 such that a patient's IGA is ≥ 3 , with the exception of patients in the baricitinib 4-mg group, they will be rerandomized automatically at a 1:1 ratio to baricitinib 2-mg QD or baricitinib 4-mg QD. Rerandomization will only occur once. Patients in the baricitinib 4-mg group will remain on 4-mg.

^g Beginning at Visit 14 (Week 52), nonresponders (IGA ≥ 3) in the placebo, baricitinib 1-mg or baricitinib 2-mg treatment groups will be rerandomized at a 1:1 ratio to baricitinib 4-mg or baricitinib 2-mg QD. Nonresponders randomized to baricitinib 4-mg at baseline will remain on 4-mg. After rerandomization, patients will remain on the same dose of baricitinib for the remainder of the study.

^h Occurs approximately 28 days after the last dose of IP. Not required for patients who have been off drug for 28 days or more at the time of their last visit.

Figure JAIN.1. Illustration of study design for Clinical Protocol I4V-MC-JAIN.

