5.1.3. Period 3: Double-Blind, Long-Term Extension

Patients who complete the study through Week 52 will progress into the double-blind long-term extension phase through Week 104 (Visit 22). Daily diary collection will continue through Week 68 (Visit 18) of Period 3.

Concomitant use of background TCS therapy will continue during this treatment period as described in Section 7.7.2.

5.1.3.1. Randomized Downtitration Substudy at Week 52

At Week 52, all patients will be evaluated for substudy eligibility. To be eligible, a patient must meet all of the following criteria:

- have an IGA 0, 1 (Responder) or 2 (Partial responder) at Week 52
- have not used high- or ultra-high potency TCS in the last 14 days (potency classification in [Appendix 7](#))
- do not currently have study drug interrupted
- have been assigned to baricitinib 2-mg or 4-mg at baseline (assessed by interactive web-response system [IWRS])

Treatment

Treatment in the substudy is illustrated in [Figure JAIN.1](#). Patients eligible for the substudy will be rerandomized at a 1:1 ratio at Week 52 based on the baricitinib treatment group assigned at baseline:

- 4-mg QD rerandomized to baricitinib 4-mg QD, or baricitinib 2-mg QD
- 2-mg QD rerandomized to baricitinib 2-mg QD, or baricitinib 1-mg QD

Note: Intensification of emollients and TCS may be continued or initiated to control worsening and unacceptable symptoms of AD any time during this treatment period. For management of TCS, follow the guidelines in [Section 7.7.2](#).

Retreatment

During the substudy, if worsening of AD symptoms occurs such that IGA increases to ≥ 3 , the patient will be automatically retreated with their presubstudy baricitinib dose. When the IGA is ≥ 3 , the investigator should reinstate background TCS therapy (e.g., triamcinolone 0.1% cream and/or hydrocortisone 2.5% ointment), provided the patients are not currently using TCS, and may prescribe high- or ultra-high-potency TCS following the guidelines for use of Rescue Therapies ([Section 7.7.5](#) [Rescue Therapy]). An unscheduled visit may be needed to assess worsening of symptoms and to perform clinical safety and efficacy assessments immediately before retreatment.

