5.1.3.2. Patients Not Eligible for the Substudy

Beginning at Week 52,

- Patients with an IGA ≥ 3 who
 - are in the baricitinib 2-mg, 1-mg, and placebo treatment groups will be automatically rerandomized at a 1:1 ratio to baricitinib 2-mg QD or baricitinib 4-mg QD.

- are in the baricitinib 4-mg treatment group will remain on 4-mg QD (see “Rescue during Period 3” Section 7.7.5.2).
- Patients with an IGA 0, 1, or 2 who
 - are in the baricitinib 4-mg or 2-mg treatment groups and who are not eligible for the substudy (i.e., have study drug interrupted at Week 52, or have received high- or ultra-high potency TCS in the previous 14 days), or are in the placebo or baricitinib 1-mg groups will continue in their current treatment group.
 - Patients who experience a worsening of symptoms of AD such that IGA increases to ≥ 3 will be rerandomized at a 1:1 ratio to baricitinib 2-mg QD or baricitinib 4-mg QD. Patients in the baricitinib 4-mg group will remain on 4-mg.

This option for rescue is only available once for each patient and will be assigned by IWRS; investigators will remain blinded to treatment assignments. The investigator may reinstate background TCS therapy (e.g., triamcinolone 0.1% cream and/or hydrocortisone 2.5% ointment), provided the patients are not currently using TCS, and may prescribe high- or ultra-high-potency TCS following the guidelines for use of rescue therapies (see Section 7.7.5).

Once a patient has an IGA ≥ 3 in Period 3, the investigator will know that a patient is on the highest dose of baricitinib that he/she will receive in the study; therefore, if AD symptoms remain unacceptable then discontinuation should be considered.

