The time period for safety analysis of the 24-week interim analysis will be following criteria whichever occurs first:

- up to last dose plus up to 30 days in the study
- the first dose in Period 3
- up to dose change or up to the data cutoff date

The time period for safety analysis of the 52-week interim analysis will be following criteria whichever occurs first:

- up to last dose plus up to 30 days in the study
- the study discontinuation date
- up to dose change
- the first dose date in Period 3

**The time period for safety analysis of the 104 interim analysis** will be following criteria whichever occurs first:

- up to last dose plus up to 30 days in the study
- the study discontinuation date
- up to dose change date due to rescue

- up to dose change date due to retreatment
- the first dose in Period 4
- up to the data cutoff date

**The time period for safety analysis of the final analysis** will be following criteria whichever occurs first:

- up to last dose plus 30 days or up to last date in the study
- the study discontinuation date
- up to dose change

**Long-Term Extension (LTE) Substudy Population:** The LTE Substudy Population is defined as the patients who received at least one study medication in Period 3 of Study JAIN, and entered the downtitration substudy. Additionally, those patients who did not met study discontinuation criteria in Period 3 and continued in Period 4 will be considered in the analysis set.

**Long-Term Extension(LTE) Substudy Relapse Population:** for a subset of patients in the LTE Substudy Population defined as above who experienced a relapse in Period 3 or Period 4 (IGA $\geq$ 3 after Week 52).

**Long-Term Extension(LTE) Non-responder Population:** The LTE Non-responder Population is defined as the patients who received at least one study medication in Period 3 of Study JAIN, and IGA $\geq$ 3 at Week 52. Additionally, those patients who did not met study discontinuation criteria in Period 3 and continued in Period 4 will be considered in the analysis set.

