**Long-Term Extension(LTE) Responders & Partial Responders who did not enter the Substudy:** This population is defined as the patients who received at least one study medication in Period 3 of Study JAIN, and were Responders (IGA 0 or 1) and Partial Responders (IGA 2) at Week 52 but were not eligible for downtitration substudy (i.e. had study drug interrupted at Week 52, or had received high or ultra-high potency TCS in the previous 14 days). Additionally, those patients who did not met study discontinuation criteria in Period 3 and continued in Period 4 will be considered in the analysis set.

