**Table JAIN.6.3. Treatment Groups and Comparisons for the 104-Week Interim and Final DBL Analysis Population**

Study Period	Analysis Population	Treatment Group	Abbreviation	Analyses Category
Long-Term Extension Period (Period 3 and Period 4)	LTE Substudy Population	Bari 4-mg in Period 2, were re-randomized to (Bari 4-mg or Bari 2-mg) in Period 3/Period 4;	Bari 4-mg/4-mg Bari 4-mg/2-mg	Efficacy
	LTE Substudy Population with IGA(0,1) at Week 52	Bari 2-mg in Period 2, were re-randomized to (Bari 2-mg or Bari 1-mg) in Period 3/Period 4.	Bari 2-mg/2-mg Bari 2-mg/1-mg	Efficacy for Subsetting IGA(0,1) at Week 52
	LTE Substudy Relapse Population	Bari 4-mg in Period 2, were re-randomized to (Bari 4-mg or Bari 2-mg) in Period 3/Period 4, retreated with presubstudy of Bari 4-mg when Relapse occurred;  Bari 2-mg in Period 2, were re-randomized to (Bari 2-mg or Bari 1-mg) in Period 3/Period 4, retreated with presubstudy of Bari 2-mg when Relapse occurred.	Bari 4-mg/4-mg/4-mg Bari 4-mg/2-mg/4-mg  Bari 2-mg/2-mg/2-mg Bari 2-mg/1-mg/2-mg	Time to Relapse
	LTE Non-responder Population	Bari 4-mg stays Bari 4-mg in Period 2 & Period 3/Period 4;	Bari 4-mg Bari 2-mg /2-mg Bari 2-mg/4-mg Bari 1-mg/2-mg Bari 1-mg/4-mg PBO/Bari 2-mg PBO/Bari 4-mg	Efficacy

	(Bari 2-mg, Bari 1-mg or Placebo) were re-randomized to (Bari 2-mg or Bari 4-mg) in Period 3.		
Long-Term Extension (LTE) Responders & Partial Responders who did not enter the Substudy	Bari 4-mg, Bari 2-mg Bari 1-mg, Placebo will continue on the same treatment	Bari 4-mg Bari 2-mg Bari 1-mg Placebo	Efficacy
Safety Population	Bari 4-mg, Bari 2-mg Bari 1-mg, Placebo who continuously got treated from baseline and censored in case of dose change.	Bari 4-mg Bari 2-mg Bari 1-mg Placebo All Bari	Safety

Abbreviations: Bari = baricitinib; IGA = Investigator's Global Assessment for AD; LTE = Long-Term Extension; PBO = placebo.

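### Read literally, SAP 6.2.1 leaves placebo and 1-mg Week 52 responders with no drug interruption or recent high-potency TCS in no extension efficacy population, because the protocol's clause adding these two arms was dropped

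*SAP*

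**What the plan says.** SAP 6.2.1 sets up three main extension populations for efficacy, each requiring at least one dose in Period 3.

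- **Substudy:** patients who were dosed "and entered the downtitration substudy". The relapse population is a subset of this one.
- **Non-responder:** patients with IGA of 3 or more at Week 52.
- **Responders and partial responders who did not enter the substudy:** the definition takes patients with IGA 0 to 2 at the Week 52 visit and adds the condition "but were not eligible for downtitration substudy (i.e. had study drug interrupted at Week 52, or had received high or ultra-high potency TCS", with a 14-day look-back for the TCS. Treatment arm is not mentioned.

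Table JAIN.6.3 describes the treatment groups for the third population as "Bari 4-mg, Bari 2-mg Bari 1-mg, Placebo will continue on the same treatment", with four separate columns.

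Protocol 5.1.3.1 makes baseline assignment to 2-mg or 4-mg a condition of substudy entry. Protocol 5.1.3.2 then describes the IGA 0 to 2 patients who stay on their current treatment in two parts. The first part covers patients described as "are in the baricitinib 4-mg or 2-mg treatment groups and who are not eligible for the substudy (i.e., have study drug interrupted at Week 52", and also those given recent high- or ultra-high-potency TCS. The second begins "or are in the placebo or baricitinib 1-mg groups will continue in their current treatment group". Footnote f to the design figure makes the same split, in the protocol and again in the SAP; it says that those "who are not eligible for the randomized downtitration substudy and those who are in the baricitinib 1-mg or placebo groups will remain on their current", meaning the dose they already take. SAP Section 5, item b, also counts placebo and 1-mg patients among the responders not eligible for the substudy.

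**The concern.** The abbreviation i.e. makes a list exhaustive. With only two reasons listed, a placebo or 1-mg responder qualifies only by having had an interruption or recent high-potency TCS. The actual reason every such patient is ineligible, the assigned arm, is missing.

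A programmer working from 6.2.1 would leave the other placebo and 1-mg responders out of every extension efficacy summary. The columns planned in Table JAIN.6.3 could still contain a few patients, so nothing in the output need reveal the error, and those few would be selected for interruption or rescue.

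The endpoints at stake are the secondary ones for patients not entered into the substudy (IGA 0/1, IGA 0/1/2 and EASI75 at Weeks 68 and 104) and the exploratory commitment to follow placebo responders in the extension. The same population also feeds Period 3 and 4 disposition (SAP 6.5), patient characteristics at the final analysis (6.6), compliance (6.7), and Tables JAIN.6.9 and JAIN.6.12. Disposition summed over the three populations would not account for everyone in the extension.

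**Working it through.** The documents give no size for this population, so there is no planned figure to reproduce beyond the arm sizes.

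**Arm sizes.** 500 patients at 1:1:2:1 gives 500 × 1/5 = 100 each for placebo, 1-mg and 4-mg, and 500 × 2/5 = 200 for 2-mg, as protocol 5.1 states. Placebo and 1-mg together are 200.

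**Membership.** Take patients with Week 52 IGA 0 to 2 who were dosed in Period 3, and cross arm with interruption at Week 52 and with recent high- or ultra-high-potency TCS. This gives 4 × 2 × 2 = 16 combinations.

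| Arm | Interruption or recent high-potency TCS | Substudy | SAP 6.2.1, literal | Protocol 5.1.3.2 |
|---|---|---|---|---|
| Placebo, 1-mg | neither | no | **out** | **in** |
| Placebo, 1-mg | either or both | no | in | in |
| 2-mg, 4-mg | neither | yes | out | out |
| 2-mg, 4-mg | either or both | no | in | in |

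The SAP and the protocol agree in 14 combinations and differ in 2: placebo with neither, and 1-mg with neither. Patients in those two cells did not enter the substudy, so they are not in that population or its relapse subset. Their Week 52 IGA is below 3, so they are not in the Non-responder population. A later rise in IGA does not move them there, because that population is fixed on the Week 52 score. They therefore belong to no extension efficacy population. Membership for 2-mg and 4-mg is the same under both readings.

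**Size.** Let f be the share of placebo and 1-mg responders with an interruption or recent high-potency TCS. The literal rule keeps f and excludes 1 − f. The documents do not give f. For illustration, also assume that 30% of the 200 placebo and 1-mg patients are IGA 0 to 2 at Week 52 and dosed in Period 3: 200 × 0.30 = 60.

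| Assumed f | Share excluded (1 − f) | Kept of 60 | Excluded of 60 |
|---|---|---|---|
| 2% | 98% | 1.2 | 58.8 |
| 5% | 95% | 3 | 57 |
| 10% | 90% | 6 | 54 |
| 20% | 80% | 12 | 48 |
| 30% | 70% | 18 | 42 |

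The assumed response rate changes the counts but not the percentage. At 20% there are 40 such responders, of whom 0.8 to 12 are kept over the same range of f; at 50% there are 100, of whom 2 to 30 are kept.

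**The case against.** The best defence is that the SAP, read as a whole, points to one population. Its title covers everyone with a response who did not enter the substudy. The governing condition is ineligibility, which placebo and 1-mg patients meet by arm under protocol 5.1.3.1; only the explanatory parenthesis is incomplete. Section 5 item b, footnote f and Table JAIN.6.3 all agree with that reading. This stands, and it means that nobody decided to exclude these patients. A reader might infer a deliberate analysis choice, but the documents do not support that. It does not make the text harmless, because 6.2.1 is the formal membership rule whereas Table JAIN.6.3 sets out the treatment groups.

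It can also be said that the table is not strictly incompatible with the literal rule, since its placebo and 1-mg columns need not be empty. That is fair. The firmer conflict is with protocol 5.1.3.2; the table shows what was intended.

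The impact is limited too. SAP 6.2.2.3 provides only descriptive statistics for Periods 3 and 4, 6.4 applies no multiplicity adjustment there, and 6.2.2 calls efficacy after Week 104 exploratory. All of this stands.

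**Conclusion.** The definition is wrong as written and should be corrected, as an internal inconsistency of modest consequence. That patients in the two cells fall outside every extension efficacy population follows from the text alone and needs no assumption about rates.

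How many patients are affected does depend on an assumption. A reader might infer that almost all placebo and 1-mg responders are lost, or about 90%. That figure needs f near 10%, and the documents do not supply f. Over an assumed 2% to 30% the exclusion runs from 98% to 70%.

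The effect is confined to the descriptive, unadjusted Period 3 and 4 summaries that use this population. The primary and key secondary analyses are unaffected, and long-term safety for placebo and 1-mg comes from the safety population, grouped by treatment from baseline.

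A reader might also infer that correcting the definition would yield an unbiased comparison across doses. It would not. The 2-mg and 4-mg members are, by design, only those interrupted or recently given high-potency TCS, and the whole set is selected on Week 52 response.

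**What to change.** Replace the parenthesis in SAP 6.2.1 with wording to this effect:

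*(i.e. were randomized at baseline to placebo or baricitinib 1-mg; or were randomized to 2-mg or 4-mg and either had study drug interrupted at Week 52 or had used high- or ultra-high-potency TCS within the preceding 14 days)*

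This restores the protocol's clause, matches Table JAIN.6.3, leaves 2-mg and 4-mg membership unchanged, and gives every placebo or 1-mg responder dosed in Period 3 a population. A table footnote should say that the 2-mg and 4-mg columns are a selected group, not comparable with placebo and 1-mg. The cost is one sentence and a footnote, plus a check that the population flag is programmed to the corrected rule. No new data are needed.
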